14.1 Definitions

The following definitions are based on:

- International Council for Harmonisation (ICH) E2A: International Conference on Harmonisation Tripartite Guideline: Clinical Safety Data Management: Definitions and Standards for Expedited Reporting (1994).
- ICH E6: International Council for Harmonisation Tripartite Guideline: Guideline for Good Clinical Practice (1996) and Integrated Addendum [E6] (R2) June 2015.
- Office of Human Subjects Protection, Division of Department of Health and Human Services Policy; "Reviewing and Reporting Unanticipated Problems Involving Risks to Subjects or Others and Adverse Events" (2007).
- Code of Federal Regulations Title 21, Part 312.32 (2011).

Also included are events that are common to this subject population.

14.1.1 Adverse Event Definition

An AE is defined as any untoward medical occurrence in a patient or clinical investigation subject administered a pharmaceutical product and which does not necessarily have to have a causal relationship with this treatment. An AE can therefore be any unfavorable and unintended sign (including an abnormal laboratory finding, for example), symptom, or disease temporally associated with the use of a medicinal (investigational) product, whether or not considered related to the medicinal (investigational) product.

14.1.2 Adverse Reaction Definition

An adverse reaction (AR) is defined as any AE caused by a drug.

In the preapproval clinical experience with a new medicinal product or its new usages, particularly as the therapeutic dose(s) may not be established, all noxious and unintended responses to a medicinal product related to any dose should be considered adverse drug

reactions. The phrase responses to a medicinal product means that a causal relationship between a medicinal product and an adverse event is at least a reasonable possibility, ie, the relationship cannot be ruled out.

14.1.3 Suspected Adverse Reaction Definition

A suspected adverse reaction is defined as an AE for which there is a reasonable possibility that the drug caused the AE. Reasonable possibility suggests a causal relationship between the study drug treatment and the AE. A suspected adverse reaction implies a lesser degree of certainty about causality than an AE.

14.1.3.1 Unexpected Adverse Drug Reaction Definition

An unexpected adverse drug reaction is defined as an adverse reaction, the nature or severity of which is not consistent with the applicable product information (eg, Investigator's Brochure for an unapproved investigational product or package insert/summary of product characteristics for an approved product).

14.1.4 Unexpected Adverse Event or Unexpected Suspected Adverse Reaction Definition

This is an AE or suspected unexpected adverse reaction (SUSAR) which is not listed in the Investigator's Brochure (IB), nor listed at the specificity or severity observed. If an AE or SUSAR is listed in the IB as occurring with a specific class of drugs, or occurring as part of a disease process, or from the pharmacological properties of the drug, but not specifically mentioned as occurring with the particular drug under investigation, it should be considered unexpected.

14.1.5 Treatment Emergent Adverse Event Definition

An AE for which the start date is on or after the date that the intervention begins.

14.1.6 Serious Adverse Event Definition

Serious adverse events (SAE) are a subset of adverse events. They are defined (in the view of the investigator or the sponsor) as any untoward medical occurrence that meets any of the following criteria:

- Resulted in death.
- Is life-threatening (if an AE or SUSAR places a subject at risk of death at the time of the event; it does not refer to an event which hypothetically might have caused death if it were more severe).
- Requires inpatient hospitalization or prolongation of existing hospitalization.
- Results in disability (persistent or significant incapacity or substantial disruption of the ability to conduct normal life functions).
- Is a congenital anomaly/birth defect.
- Is an important medical event that may not result in death, be life-threatening, or require hospitalization may be considered serious when, based upon appropriate medical judgment, they may jeopardize the subject and may require medical or surgical intervention to prevent one of the outcomes listed in this definition. Examples of an important medical event include: allergic bronchospasm, blood dyscrasias, convulsions that do not result in inpatient hospitalization, or drug dependence/abuse.

14.1.7 Severity of an Adverse Event

Intensity of an AE, assessed by the investigator and graded as mild, moderate or severe, irrespective of the relationship to the drug or seriousness of the event, and evaluated according to the following scales:

- Mild awareness of the symptom but easily tolerated.
- Moderate discomfort enough to interfere with normal activities.
- Severe Incapacitating with the inability to perform normal activities.

An AE not listed in the IB at the specificity or severity observed is considered unexpected.

14.1.8 Study Drug Causality

Study drug causality will be assessed as follows:

Unrelated: An AE that is clearly and incontrovertibly due to extraneous causes (disease, environment, etc) and does not meet the criteria for 'possible' or 'probable.'

Possible: The connection between the AE and study treatment appears unlikely, but cannot be ruled out with certainty. An AE may be considered 'possibly related' if it has at least 2 of the following:

- It follows a reasonable temporal sequence from administration of study drug.
- It may readily have been produced by the subject's clinical state or by environmental or toxic factors.
- It follows a known response pattern to study drug.

Probable: An AE that is considered to be related to study drug treatment with a high degree of certainty. An AE may be considered probably related if:

- It follows a reasonable temporal sequence from administration of study drug.
- It cannot be reasonably explained by the known characteristics of the subject's clinical state.
- It follows a known pattern of response to study drug treatment.
- It reappears upon rechallenge.

Table 14–1 lists adverse events that are common in this subject population (ie, with HRS), even in the absence of exposure to the study drug (Rozov-Ung and Panesar, 2010; Arroyo et al, 2008). The investigator may use this as a guidance while assessing the causality. Adverse events will be analyzed in both an aggregate and individual manner. However, if it is deemed an AR, the sponsor will follow the appropriate procedures to communicate and report the AR.

Table 14–1: Adverse Events Common to the Hepatorenal Syndrome (HRS) Population

MedDRA System Organ Class	Preferred Term
Blood and Lymphatic System Disorders	anemia
	coagulopathy
Cardiac Disorders	atrial fibrillation
	bradycardia
Gastrointestinal Disorders	abdominal pain
	diarrhea
	nausea
	vomiting
General Disorders and Administration Site Conditions	multi-organ failure
Hepatobiliary Disorders	hepatic failure
Infections and Infestations	pneumonia
	urinary tract infection
Metabolism and Nutrition Disorders	hyperglycemia
Nervous System Disorders	headache
Respiratory, Thoracic and Mediastinal Disorders	dyspnea
	epistaxis
	pulmonary edema
	respiratory failure
Vascular Disorders	hypotension

Source: Rozov-Ung and Panesar, 2010; Arroyo et al, 2008.

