5.3.3 Safety

Most subjects in both treatment groups in the OT-0401 and REVERSE studies experienced at least 1 adverse event (AE), which is expected given the high incidence of disease-related events in this severely ill patient population. The most commonly observed adverse reactions in terlipressin-treated subjects were abdominal pain and diarrhea (refer to Table of Adverse Drug Reactions in the Investigator's Brochure). Less common adverse reactions with clinical significance that were reported in terlipressin-treated subjects include: wheezing, respiratory failure, peripheral ischemia manifested as skin necrosis, peripheral coldness, livedo reticularis and Raynaud's phenomenon; intestinal ischemia including ischemic colitis; myocardial ischemia including myocardial infarction. The safety characteristics of terlipressin in the 2 studies were consistent with its vasoconstrictor mechanism of action. None of the events leading to discontinuation of terlipressin in either study were fatal and all resolved afterwards. Refer to the Investigator's Brochure for further details.

The safety characteristics of terlipressin observed in the 3 randomized, controlled trials is consistent with the established safety profile of terlipressin from 30 years of clinical experience, as captured in the literature and post-marketing data from the World Health Organization (WHO) database. There were no new, unusual or unexpected AEs observed in the clinical studies compared to the published data.

For detailed terlipressin safety risk profiling, please refer to the Investigator's Brochure.

In general, terlipressin has a well-established safety profile in the treatment of patients with HRS Type 1. The safety risks are predictable and recognizable. The adverse drug reactions can be readily managed and reversed by terlipressin dose reduction or interruption in hospital-care settings.

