10.3.2 Dose Modifications

- If SCr has decreased, but by less than 30% from the baseline value on Day 4 after a minimum of 10 doses of study drug, the dose of study drug will be increased to 2 mg every 6 hours (± 30 minutes) (8 mg/day).
- The dose should not be increased in subjects with coronary artery disease or in the setting of circulatory overload, pulmonary edema, or bronchospasm.
- If dosing is interrupted due to an adverse event, study drug may be re-started, at the discretion of the investigator, at the same or lower dose as per protocol (refer to Section 10.3.2.1). Study drug will not be restarted if dosing was interrupted due to cardiac ischemia or mesenteric ischemia.
- If in the investigator's judgment, a dose increase is not advisable or otherwise justified in the individual subject, the reason(s) for not increasing the dose of study drug will be documented on the electronic case report form (eCRF).

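### The causality categories in Section 14.1.8 are not exhaustive: a new, unexplained event that follows dosing can fit none of them, while a ready disease explanation counts towards relatedness

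*Combined protocol and SAP*

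**What the plan says.** Section 14.1.8 has three causality categories.

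- *Unrelated* needs a plain and indisputable outside cause, and the event must also fail the other two categories. It is therefore not a default.
- *Possible* is introduced as a link that seems improbable but cannot be excluded. It then sets a count: an event qualifies "if it has at least 2 of the following". The three items are a reasonable time sequence after study drug, a known response pattern, and this one: "It may readily have been produced by the subject's clinical state or by environmental or toxic factors".
- *Probable* is for a high degree of certainty. It lists four items: timing, no reasonable explanation in the clinical state, a known response pattern, and "It reappears upon rechallenge". It does not say whether all, any or some number of them are required.

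Section 10.3.2 states: "Study drug will not be restarted if dosing was interrupted due to cardiac ischemia or mesenteric ischemia". Section 10.4 requires permanent discontinuation after such an event. Section 5.3.3 names intestinal and myocardial ischemia among the reactions already reported with terlipressin.

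The general threshold also varies. Section 14.1.3 reads: "A suspected adverse reaction is defined as an AE for which there is a reasonable possibility that the drug caused the AE". Section 14.1.2 likewise counts a reaction when the relationship cannot be excluded. The opening of Section 14 instead asks the investigator for a 'reasonable probability'.

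**The concern.** An alternative explanation normally argues against a drug cause. In the Possible list it argues for one. The event that most looks like a new toxicity (after dosing, not explained by the disease, not seen before) fails the count, and the same event with a disease explanation passes it.

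The rating is used. Section 15.1 classifies adverse events by the investigator's view of relationship. Section 14.1.8 makes sponsor communication depend on an event being deemed an adverse reaction. Section 14.3.3 holds serious events that are Section 6.1 study endpoints for the final report unless they are unusual and unexpected and there is evidence of a causal link. Section 6.1.5 lists serious adverse events and mortality, so that clause could reach widely. An event not listed in the Investigator's Brochure will usually also lack a known response pattern, which is the case the scale handles worst.

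**Working it through.** The plan gives no figure to reproduce; this is a check of the rules.

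**Inputs**, all from Section 14.1.8, each coded 1 if present and 0 if not: T = timing; C = explainable by the clinical state or other outside factors; K = known pattern; R = recurs on rechallenge. The Probable item on lack of explanation is taken as 1 − C.

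**Rules**

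- Possible: T + C + K ≥ 2.
- Probable: T + (1 − C) + K + R ≥ k. The section gives no k, so k = 1 to 4 were all run.
- Unrelated: C = 1 and neither rule above met. Treating any C as an indisputable outside cause is generous, because it fills the category as far as it can be filled.

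**Key cases** (the highest category reached is shown)

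| Event | T, C, K, R | Possible items | Probable items | k = 4 | k = 3 | k = 2 |
|---|---|---|---|---|---|---|
| New, unexplained | 1, 0, 0, 0 | 1 of 3 | 2 of 4 | none | none | Probable |
| Same, recurs on rechallenge | 1, 0, 0, 1 | 1 of 3 | 3 of 4 | none | Probable | Probable |
| Same timing, disease-explained, no known pattern | 1, 1, 0, 0 | 2 of 3 | 1 of 4 | Possible | Possible | Possible |
| Ischemia, unexplained, rechallenge barred | 1, 0, 1, 0 | 2 of 3 | 3 of 4 | Possible | Probable | Probable |
| Ischemia, explainable, rechallenge barred | 1, 1, 1, 0 | 3 of 3 | 2 of 4 | Possible | Possible | Probable |

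The first and third rows differ only in C. Changing C from 0 to 1 raises the Possible score from 1 to 2, and the event passes.

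**All 16 combinations**

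| Probable items required | No category, of 16 | Of the 8 with T = 1 |
|---|---|---|
| 4 | 6 | 2 |
| 3 | 4 | 1 |
| 2 | 1 | 0 |
| 1 | 0 | 0 |

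At k = 4, 1 combination is Probable, 7 are Possible only and 8 are neither. Two of those 8 have a disease explanation and nothing else towards Possible, so Unrelated can take them: 8 − 2 = 6. All 6 have C = 0. The two with timing are the first two rows of the case table. At k = 4 no combination with R = 0 is Probable. These are counts of logical cases, not expected rates of events.

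**Which k?** Possible states a minimum count and Probable does not, and Probable claims a high degree of certainty. Both point to all four items. A threshold of 1 or 2 fits that certainty poorly: at k = 1 even the disease-explained event in the third row would be Probable.

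**The case against.** The strongest reply is that the protocol nowhere says all four Probable items are needed. If three suffice, the rechallenge-positive event and unexplained ischemia both reach Probable. That stands, so the statements about rechallenge and ischemia are conditional. It does not rescue the new, unexplained event without rechallenge, which fails at three as well as at four.

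The wording is also permissive, the bar for Unrelated is very high, and both the opening of Possible and Section 14.1.2 lean towards relatedness. An investigator could use Possible despite the count. That stands too: how sites would code the unplaced event is unknown.

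A reader might infer that related-event tables will understate ischemia. The documents do not support this. Ischemia is a known pattern, so with timing it always meets at least 2 of 3 and stays Possible, which is a related grade. At most it is graded lower, and no table restricted to Probable events is specified.

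A reader might also infer that Table 14-1, which lists events common in this population, steers known reactions out of the related grades. It includes abdominal pain and diarrhea, although Section 5.3.3 says: "The most commonly observed adverse reactions in terlipressin-treated subjects were abdominal pain and diarrhea". But the table is optional ("The investigator may use this as a guidance while assessing the causality"), and under the section's own count a disease explanation adds a point. A term with timing, a known pattern and a disease explanation meets 3 of 3.

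Finally, the reach is limited. Section 14.3.1 has sites report every serious event regardless of relatedness, a DSMB reviews safety data (Section 14), and the frequency summaries in Section 15.3.6.4 do not use causality. All of this stands.

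**Conclusion.** The defect is real and is one of drafting. On any reading, the Possible count rejects a new, unexplained event with the right timing and accepts its disease-explained counterpart. That event has no category unless 2 or fewer Probable items suffice. If all four are required, which is the natural reading but not a stated one, positive rechallenge does not help it, and cardiac or mesenteric ischemia cannot rise above Possible.

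The size is 6 of 16 combinations without a category at four items (2 of 8 with timing) and 4 of 16 at three items (1 of 8). These counts rest on coding each item as yes or no and on the generous treatment of Unrelated.

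It is tempting to conclude that drug-related events will be systematically under-classified. That is not shown. The unplaced event is unclassifiable rather than Unrelated, and the clinical-state item also moves disease-explained events up to Possible. The supported statement is that such events can be misclassified or left without a grade in causality-based tabulations and causality-dependent reporting. The randomized comparison of event frequencies is untouched. The wording should be corrected, but the point does not threaten the trial's main safety comparison.

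**What to change.** Change the wording of Section 14.1.8 and one phrase in Section 14. The restart and discontinuation rules in Sections 10.3.2 and 10.4 stay as they are.

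1. Stop counting a ready explanation in the clinical state towards relatedness.
2. Let Possible cover any event that does not reach Probable and whose relationship to study drug cannot be excluded. With Unrelated kept for clearly extraneous causes, the three categories are then exhaustive.
3. State how many Probable items are required. Treat rechallenge as supportive, and record it as not assessable where restart is barred.
4. Align the 'reasonable probability' in the opening of Section 14 with the 'reasonable possibility' in Sections 14.1.2 and 14.1.3.

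A new yes/no causality scale is not needed, nor is removing terms from Table 14-1.

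The cost is protocol and eCRF-guideline wording plus a site memo, with no new data. Counts of related events will differ somewhat. The Amendment 3 text refers to subjects enrolled on or after 17 August 2018, so enrollment appears to have been under way when the current version was written. Events already coded under the existing wording would need a note in the report or a re-review.

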14.1.9 Overdose

Overdose is defined as an accidental or intentional/infusion or excessive dose of a product.

14.2 Collection of Adverse Events/Serious or Unexpected

Any AE occurring prior to signing the ICF should be considered medical history or a pre-existing condition and will be collected on the Medical History eCRF.

All AEs will be assessed and recorded beginning with study drug administration until 7 days after discontinuation of study drug and at each evaluation. Adverse events considered serious will be assessed and recorded until 30 days after discontinuation of study drug, excluding deaths, which will be collected up to 90 days after the first dose of study drug.

The investigator will collect and record all necessary data including investigations that were performed for any AE of special interest, ie, an ischemic abdominal event, ischemic cardiac event, or bronchospasm-related respiratory event.

14.2.1 Laboratory Abnormalities

The investigator will review clinical laboratory test results in a timely fashion. Laboratory abnormalities deemed clinically significant will be recorded as AEs (as defined above) on the eCRF. Those events considered serious should be reported to the sponsor as outlined in Section 14.3.1.

14.2.2 Hospitalizations

Planned hospital admissions and/or planned surgical operations for an illness or disease, which existed before the subject was randomized are not to be considered AEs (eg, re-hospitalization for liver transplantation). However, a baseline condition which deteriorates during the clinical study may be considered an AE.

Following the initial hospital discharge, all re-hospitalizations within 30 days post end of treatment (except for planned hospital admissions or procedures as described above) are to be recorded as a serious AE. Re-hospitalizations will require an investigator assessment and opinion regarding possible recurrence of HRS Type 1.

14.2.3 Complications of the Disease

Complications frequently associated with HRS Type 1 are expected to occur, but should be recorded as an AE or serious AE, as applicable, eg, EVH, hepatic encephalopathy, sepsis, pneumonia, urinary tract infection.

Since HRS Type 1 is the indication under investigation, worsening or aggravation of HRS during the active treatment period (including non-response) will NOT be recorded as a serious AE unless HRS is the cause of death or results in a subsequent re-hospitalization due to suspected recurrence.

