Treatment should be continued until 24 hours after a second consecutive SCr value no more than 1.5 mg/dL has been obtained, OR up to a maximum of 14 days (maximum of 15 days if SCr first reaches 1.5 mg/dL on Day 14).

If on Day 4 (after a minimum of 10 doses) SCr is at or above baseline value, study drug should be discontinued. Treatment must be discontinued when the subject is to undergo RRT, liver transplantation, TIPS or vasopressor

therapy.

Dosing must be permanently discontinued if an event of cardiac ischemia or mesenteric ischemia occurs.

Retreatment

If judged by the investigator to be potentially beneficial, subjects who demonstrate at least a partial response during the initial treatment course (at least 30% reduction in SCr) who develop recurrence of HRS Type 1 during the study or follow-up period may be retreated with initially assigned blinded study drug for a maximum of 14 days (from the beginning of the retreatment, treatment and study procedures will be identical to the initial therapy). To qualify for retreatment the subject must again meet the study inclusion/exclusion criteria and the sponsor must be contacted prior to initiation of retreatment. Retreatment may occur within 90 days of the subject's first dose of study drug. Subjects will not be re-randomized or re-stratified for the retreatment cycle.

Duration of Treatment:

The active treatment period will be 14 days (exception: 15 days as described above), allowing 1 retreatment cycle. Subjects will have a scheduled follow-up visit for Day 30 (± 10), and will be contacted by phone for Day 60 (± 14), and Day 90 (± 14).

Criteria for Evaluation:

Primary Efficacy Endpoint:

Incidence of verified HRS reversal, defined as the percentage of subjects with 2 consecutive SCr values no more than 1.5 mg/dL at least 2 hours apart, while on treatment by Day 14 or discharge (on treatment defined as up to 24 hours after the final dose of study drug). Subjects must be alive without RRT for at least 10 days after achieving verified HRS reversal. SCr values after RRT, TIPS, liver transplant, or open-label vasopressor use will be excluded from primary end point analysis. SCr values obtained after midodrine administration will be included if midodrine was started on Day 1, was administered for no more than 24 hours, and the subject was enrolled on or after 17 August 2018. SCr values will also be included if obtained after the administration of a single dose of dobutamine.

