5.3.2 Efficacy

Improvement in renal function is the goal of therapy for HRS Type 1; improvement in renal function is associated with improvement in clinical outcomes and improved prognosis, with or without liver transplantation. HRS reversal is a widely accepted, clinically meaningful response to treatment for HRS Type 1, as apparent inexorable, rapid progression of renal failure is arrested and normal renal function in the setting of decompensated liver disease is restored. The primary endpoint of HRS reversal (1 serum creatinine [SCr] value of no more than 1.5 mg/dL) is the standard endpoint utilized in the literature and HRS treatment guidelines (Arroyo et al, 1996; Salerno et al, 2007; Angeli et al, 2015).

The OT-0401 study (112 subjects with HRS Type 1 randomized 1:1 to receive terlipressin or placebo, with concomitant albumin administration recommended in both treatment arms) demonstrated a significantly higher rate of HRS reversal (34% vs 13%, p = 0.008) in the terlipressin treatment group compared to the placebo group. The primary endpoint of Treatment Success at Day 14 (an initial reduction of SCr to no more than 1.5 mg/dL followed by a confirmatory SCr measurement of no more than 1.5 mg/dL 48 hours after the initial HRS reversal and an additional SCr value less than 2.5 mg/dL at Day 14, without intervening liver transplant or dialysis) was also met following the incorporation of additional SCr values post initial database closure (29% vs 13%, p = 0.037). Furthermore, the prespecified endpoint of change in SCr from baseline to Day 14 demonstrated a greater reduction in SCr with terlipressin vs placebo (-0.9 mg/dL; p = 0.0008).

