13.2.3 Active Study Period (14 Days)

13.2.3.1 Dosing (Up to 14 Days)

The active study period extends from the initiation of study treatment through Day 14 (Day 15 as described in Section 10.4) or discharge from the hospital for any reason, whichever occurs first. Study drug will be administered as described in Section 10.3. Concomitant medications will be collected during this active study period.

See Table 13–1 for the schedule of assessments during the active study period.

13.2.3.2 End of Treatment, Discharge or Day 14

Treatment should be continued until 24 hours after 2 consecutive SCr values no more than 1.5 mg/dL have been obtained, OR up to a maximum of 14 days (maximum of 15 days if SCr first reaches 1.5 mg/dL on Day 14, when the Day 14 assessments will be performed on Day 15).

Following HRS reversal (SCr no more than 1.5 mg/dL), repeat values for SCr must be obtained a minimum of 2 hours after the first SCr value. Every effort must be made to collect these SCr values.

All information regarding paracentesis events, RRT, TIPS, liver transplant, or open-label vasopressor use must be collected.

The subject will be contacted to determine the status of survival without RRT at 10 days after the second SCr value no more than 1.5mg/dL is attained.

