15.1 Safety Variables

Safety variables will include the following:

- Adverse events.
- Serious adverse events, including deaths.
- Vital signs (body temperature, blood pressure, heart rate, respiratory rate, and SpO₂).
- MELD score.
- Encephalopathy score.
- Laboratory parameters other than SCr.

Adverse events will be collected from the start of study drug administration, during treatment and up to 7 days post end of treatment and at each evaluation. Adverse events considered serious will be collected up to 30 days after the end of treatment. Deaths up to 90 days will be reported as SAEs. Adverse events will be classified by Medical Dictionary for Drug Regulatory Activities (MedDRA) system organ class, preferred term, severity, and seriousness, as well as by the investigator's assessment of the relationship of the AE to the study drug.

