15.3.6.4 Safety Analyses

Continuous variables will be summarized by N, mean, standard deviation, median, minimum and maximum. These include:

- Change from baseline in MELD score.
- Change from baseline in encephalopathy score.
- Change from baseline in BUN.
- Daily values, daily averages, and change from baseline of vital signs of body temperature, systolic blood pressure, diastolic blood pressure, heart rate, respiratory rate, SpO₂, and MAP.
- Change from baseline in laboratory values.

Laboratory shift tables will be created.

Adverse events will be summarized by frequency and percentage of subjects.

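### The any-SAE percentage counts HRS readmission but not non-fatal in-hospital HRS worsening during treatment, so it captures serious renal worsening differently by response

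*Combined protocol and SAP*

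**What the plan says.** Section 14.2.3 exempts disease progression on treatment from SAE recording. It names "worsening or aggravation of HRS during the active treatment period (including non-response") and says that such an event "will NOT be recorded as a serious AE unless HRS is the cause of death or results in a subsequent re-hospitalization due to suspected recurrence". The Synopsis gives the length of that period: "The active treatment period will be 14 days", with 15 days as a stated exception. Section 13.2.3.1 defines a similarly named period that can end sooner: "The active study period extends from the initiation of study treatment through Day 14" (Day 15 in the exception) or until discharge, whichever is first.

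Section 14.2.2 governs what follows discharge: "all re-hospitalizations within 30 days post end of treatment", apart from planned admissions, are SAEs, and each needs the investigator's opinion on possible recurrence. The rule applies to any discharged subject, whatever the response. Section 10.5 defines recurrence by Day 30 as a new episode after verified reversal, and counts as recurrence any case where the investigator cannot rule it out. The general SAE definition in 14.1.6 includes a prolonged hospital stay, and 14.2 collects SAEs to 30 days after the last dose.

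On analysis, 15.1 lists "Serious adverse events, including deaths" and classifies events by MedDRA system organ class, preferred term, severity, seriousness and relationship. Section 15.3.6.4 says "Adverse events will be summarized by frequency and percentage of subjects". No readable text plans an SAE summary with and without HRS events, or one that sets HRS SAEs beside the renal outcomes that 14.2.3 leaves out.

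**The concern.** Take two subjects with non-fatal renal deterioration. One never improves, and worsens in hospital within the 14 days, even to RRT or a longer stay; 14.2.3 keeps this out of the SAE data. The other reverses, goes home and is readmitted with renal worsening; this is an SAE. Which event is recorded turns on whether the subject was discharged first, a post-randomization outcome that treatment is expected to influence. Section 5.3.2 reports that OT-0401 "demonstrated a significantly higher rate of HRS reversal (34% vs 13%, p = 0.008"), and that REVERSE had 24% vs 15%.

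If reversal makes discharge more likely, both halves of the rule lean the same way. More terlipressin subjects are exposed to a readmission SAE, and more placebo subjects have in-hospital worsening that is not recorded as one. Safety is part of the trial's objective and the data are meant to support an NDA. An any-SAE excess on terlipressin could include a part that is not toxicity, and a reader who takes the percentage as the total of serious renal events would miss the in-hospital part.

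**Working it through.** **The rules side by side (non-fatal HRS worsening)**

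| Situation | SAE? | Section |
|---|---|---|
| In hospital, within the active treatment period | No | 14.2.3 |
| In hospital, after Day 14/15, stay prolonged | Can be, to 30 days after last dose | 14.1.6, 14.2 |
| Unplanned readmission within 30 days of end of treatment, responder or not | Yes | 14.2.2 |

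Fatal HRS is an SAE in either arm.

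**The plan's own figures.** The documents give no SAE, discharge or readmission rate for this trial. The arm-specific reversal scenarios in the statistical plan are in Table 15-2, so I checked those before using them. Pooled two-proportion Z:
- Scenario 1, 34/100 vs 6/50: pooled rate 40/150 = 0.2667; Z = 0.22 / √(0.2667 × 0.7333 × 0.03) = 2.8723, as stated.
- Scenario 2, 36/100 vs 7/50: Z = 2.8088 against 2.8098 stated, a trivial difference.

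**Inputs for the illustration**
- Reversal rate r: 34% vs 12% (Table 15-2, Scenario 1).
- dR, share of responders discharged: 60-90% (assumption).
- dN, share of non-responders discharged: 0, 30%, or equal to dR (assumption).
- h, share of discharged subjects readmitted for HRS: 10-30%, the same for all (assumption).
- b, background rate of any other SAE: 40-65%, equal in both arms and independent (assumption).
- w, share of non-responders who worsen non-fatally in hospital: 10-50% (assumption).

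**Step 1: HRS re-hospitalization SAEs.** Per arm: r·dR·h + (1−r)·dN·h. The gap is therefore 0.22 × (dR − dN) × h.

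| dN | Smallest gap (dR 0.6, h 0.1) | Largest gap (dR 0.9, h 0.3) |
|---|---|---|
| 0 | 2.0% vs 0.7%: 1.3 points | 9.2% vs 3.2%: 5.9 points |
| 30% | 4.0% vs 3.4%: 0.7 points | 15.1% vs 11.2%: 4.0 points |
| equal to dR | 0 | 0 |

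With dN = 0 and the reversal rates of the earlier trials, the gap is 0.21 × 0.06 to 0.21 × 0.27 = 1.3 to 5.7 points (OT-0401) and 0.09 × 0.06 to 0.09 × 0.27 = 0.5 to 2.4 points (REVERSE).

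**Step 2: any SAE.** The summary counts subjects, so a readmission adds to it only for someone with no other SAE: gap × (1 − b). In the extreme case dN = 0 this runs from 1.32 × 0.35 = 0.46 to 5.94 × 0.60 = 3.56 points.

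**Step 3: the part not recorded.** In-hospital worsening without an SAE is (1−r)·w: 19.8% vs 26.4% at w = 0.3, and 33.0% vs 44.0% at w = 0.5.

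**Step 4: both sides counted, dN = 0.** The gap becomes 0.22 × (dR·h − w), with dR·h from 0.06 to 0.27:
- w = 0.1: −0.9 to +3.7 points
- w = 0.3: −5.3 to −0.7 points
- w = 0.5: −9.7 to −5.1 points

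The sign turns in terlipressin's favour whenever w exceeds dR·h.

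**The case against.** The case on the other side is substantial.

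- **One rule, applied blind in both randomized arms.** A reader might infer that the arms' SAE percentages are not comparable. The documents do not support that: the percentages validly compare the event as defined. What fails is reading them as toxicity alone or as all serious renal worsening. Blinding does not cure that, because capture differs through response and discharge, not through knowledge of the arm.
- **Discharge is the direct gate.** A reader might infer that response itself creates the chance of this SAE. Section 14.2.2 covers a readmitted non-responder equally, and the gap is zero if non-responders go home as often. Response matters only so far as it makes discharge more likely, which is plausible but not documented.
- **The exemption is time-limited.** A reader might infer that non-fatal worsening is an SAE only through readmission. After Day 14/15 the ordinary definition applies to subjects still in hospital.
- **HRS events are not hidden.** Section 15.1 classifies by preferred term and seriousness, so HRS SAEs should be visible by term. That row would hold only the recorded side, however. RRT, TIPS, transplant and death are recorded for everyone (Table 13-1), and SCr daily to Day 14 or discharge, but no readable analysis joins these to the SAE table. Parts of the plan are blacked out.
- **The effect is small against sampling error.** With 200 vs 100 subjects and a 40% rate, the 95% margin on an arm difference is 1.96 × √(0.24 × (1/200 + 1/100)), about ±12 points. No test of AEs is specified. This stands, and it keeps the point modest.
- **Taking HRS events out of the main SAE row has its own bias.** Section 10.5 counts a recurrence that cannot be ruled out, so ambiguous readmissions, possibly drug-related, would leave the main row, probably more often in the arm with more reversals. The present rule leans against terlipressin and so is conservative for safety. This stands, and it is why the all-SAE row should remain the main one.

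**Conclusion.** The point holds as a matter of interpretation and presentation. Non-fatal HRS worsening in hospital during the active treatment period is left out of the SAE count while unplanned readmission is included, and no readable analysis treats the two consistently. The likely direction, for non-fatal HRS events, is against terlipressin. On HRS re-hospitalization SAEs the illustrated gap is about 0 to 6 points; on any SAE it is about 0.5 to 3.6 points in the extreme case and less otherwise. Only the reversal rates come from the documents; discharge, readmission, worsening and background SAE rates are assumptions, so these are ranges of what could happen, not estimates.

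Two limits apply. HRS deaths count in both arms, and if reversal prevents some of them, that works the other way in the any-SAE total. The conclusion also takes the active treatment period as the Synopsis's 14 days. If sites read it as ending with the last dose, the exemption is shorter and the effect smaller.

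**What to change.** In 15.3.6.4, for the safety population:

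1. Keep the percentage with any SAE as the main row, unchanged.
2. Add a second row by arm that excludes SAEs of HRS worsening or recurrence, identified by preferred term together with the investigator's recurrence assessment that 14.2.2 already requires.
3. Beside it, show by arm, for all treated subjects, HRS SAEs, RRT starts (recorded throughout under Table 13-1) and HRS deaths (from the immediate cause of death in 14.3.1).
4. State that readmissions where recurrence merely cannot be excluded stay visible in the all-SAE row.

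The cost is one extra descriptive table and some reliance on investigator attribution for the second row. Worsening short of RRT that never became an SAE would still be outside the table. Site reporting under 14.2.2 and 14.2.3 does not change and no new data are needed.
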